8.2. Secondary endpoints

Phase I / Dose escalation part

- Preliminary signs of antitumor activity in terms of:
 - Best overall response is defined as the best response recorded from the start of the study treatment until the end of treatment taking into account any requirement for confirmation as per RECIST v1.1 criteria ([appendix 3](#)):
Following RECIST v1.1 recommendations:
 - The best overall response is determined once all the data for the patient is known.
 - Claimed responses will have to be confirmed at least 4 weeks later to ensure responses identified are not the result of measurement errors.
 - Objective response rate (ORR) is defined as the proportion of patients with complete response or partial response according to RECIST v1.1 criteria ([appendix 3](#)). ORR under treatment and 6-month ORR will be reported. ORR under treatment is recorded from study treatment initiation until the end of treatment. Following RECIST v1.1 recommendations:
 - ORR under treatment is determined once all the data for the patient is known.
 - Claimed responses will have to be confirmed at least 4 weeks later to ensure responses identified are not the result of measurement errors.
 - Progression-free rate (PFR) is defined as the proportion of patients with complete response, partial response or stable disease more than 24 weeks as defined as per RECIST v1.1 criteria ([appendix 3](#)). 6-month PFR will be reported. . Following RECIST v1.1 recommendations, claimed responses will have to be confirmed at least 4 weeks later to ensure responses identified are not the result of measurement errors.
 - Progression-free survival (PFS) is defined as the time from study treatment initiation to the first occurrence of disease progression or death (of any cause), whichever occurs first. 1-year PFS rate will be reported.
 - Overall Survival (OS) is defined as the time from study treatment initiation to death (of any cause). 1-year OS rate will be reported.
- Pharmacodynamic study:
 - Blood samples:
 - Serum level of cytokines, kynurenine and immunophenotyping of circulating immune cells
 - Analyses of circulating DNA for identification and monitoring of mutations observed at the level of the circulating tumor cells (liquid biopsies concept).
 - Tumor samples: Fresh pre-treatment and on-treatment tumor biopsies will be performed. Samples will be formalin fixed and paraffin-embedded or fresh frozen, and will be analyzed for:
 - Hematoxylin and eosin staining (H&E).

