APPENDIX 3: EVALUATION OF RESPONSE. THE RECIST

Response and progression will be evaluated in this study using the new international criteria proposed by the revised Response Evaluation Criteria in Solid Tumors (RECIST) guideline (version 1.1) [Eur J Ca 45:228-247, 2009]. Changes in only the largest diameter (unidimensional measurement) of the tumor lesions are used in the RECIST criteria.

DEFINITIONS

Evaluable for toxicity: All patients will be evaluable for toxicity from the time of their first treatment with study drugs.

Evaluable for objective response: Only those patients who have measurable disease present at baseline, have received at least one cycle of therapy, and have had their disease re-evaluated will be considered evaluable for response. These patients will have their response classified according to the definitions stated below. (Note: Patients who exhibit objective disease progression prior to the end of cycle 1 will also be considered evaluable.)

DISEASE PARAMETERS

Measurable disease. Measurable lesions are defined as those that can be accurately measured in at least one dimension (longest diameter to be recorded) as ≥ 20 mm by chest x-ray, as ≥ 10 mm with CT scan, or ≥ 10 mm with calipers by clinical exam. All tumor measurements must be recorded in millimeters (or decimal fractions of centimeters).

Note: Tumor lesions that are situated in a previously irradiated area are not considered measurable.

Malignant lymph nodes. To be considered pathologically enlarged and measurable, a lymph node must be >15 mm in short axis when assessed by CT scan (CT scan slice thickness recommended to be no greater than 5 mm). At baseline and in follow-up, only the short axis will be measured and followed.

Non-measurable disease. All other lesions (or sites of disease), including small lesions (longest diameter <10 mm or pathological lymph nodes with ≥ 10 to <15 mm short axis), are considered non-measurable disease. Bone lesions, leptomeningeal disease, ascites, pleural/pericardial effusions, lymphangitis cutis/pulmonitis, inflammatory breast disease, and abdominal masses (not followed by CT or MRI), are considered as non-measurable.

Note: Cystic lesions that meet the criteria for radiographically defined simple cysts should not be considered as malignant lesions (neither measurable nor non-measurable) since they are, by definition, simple cysts.

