2.3 Dose escalation part/ Assessable for safety

The following patients will not be included in the population assessable for safety (primary analysis) and thus will be replaced:

- Patients who received $\leq 75\%$ RDI (Relative Dose Intensity) for trabectedin OR $\leq 75\%$ RDI for durvalumab over cycle 1, due to drug-related AE not considered as DLT.
- Patients who goes off treatment over cycle 1 for reasons unrelated to toxicity (DLT or any other AE), e.g. progression, lost to follow-up, will be replaced.

Population assessable for safety (primary analysis): all patients who completed the DLT assessment period or who developed DLT are included in the analysis.

CREATION OF A NEW INDICATOR VARIABLE

New binary variable TOL

Label: « Assessable for Safety»

TOL = 1 if the patient is assessable for safety (primary analysis)

TOL = 0 if the patient is not assessable for safety (primary analysis)

Criteria	eFORM variable	Control / program
Patient received $\leq 75\%$ RDI (Relative Dose Intensity) for trabectedin OR $\leq 75\%$ RDI for durvalumab over cycle 1, due to drug-related AE not considered as DLT	CYCLE 1 – DAY 1 AND DAY 2 (WEEK1) TREATMENT Trabectedin DOSE_TRA (dose) VPRE_TRA (volume of preparation) VOL_TRA (administered volume) WHY_TRA (2=AE related to treatment) Durvalumab DOSE_DU VPRE_DU VOL_DU WHY_DU DOSE-LIMITING TOXICITY FORM DLT_CYC OCC_CYC REL_ST	IF Trabectedin $((\text{Dose effectivement reçue VPRE_TRA and VOL_TRA/DOSE_TRA}) \leq 75\% \text{ AND INT_TRA} = 1 \text{ AND WHY_TRA} = 2 \text{ AND DLT_CYC} = 0)$ OR Durvalumab $((\text{Dose effectivement reçue VPRE_DU and VOL_DU / 1120 mg}) \leq 75\% \text{ AND INTER_D} = 1 \text{ AND WHY_DU} = 2 \text{ AND DLT_CYC} = 0)$ THEN TOL = 0
Patient goes off treatment over cycle 1 for reasons unrelated to toxicity (DLT or any other AE), e.g. progression, lost to follow-up	DISCONTINUATION VISIT END OF TREATMENT / end of treatment form DT_SOT DT_EOT EOTREASO DISCONTINUATION VISIT END OF TREATMENT / visit DIS_TRT TRA_EOT DUR_EOT DOSE-LIMITING TOXICITY FORM DLT_CYC AE FORM NUMAE AEVENT DT_AE MAX_INT TRA_MOD DUR_MOD	$\text{DT_EOT-DT_SOT} \leq 21 \text{ days}$ AND EOTREASO NOT IN (4 12) AND DLT_CYC=0 Additional control if $\text{DT_EOT-DT_SOT} \leq 21 \text{ days}$ 
 - Listing Other reason - Listing visit of end of treatment: DIS_TRT / TRA_EOT / DUR_EOT - Listing AE with TRA_MOD IN=3 OR DUR_MOD=3 THEN TOL=0

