2.4 Expansion cohort/ Evaluable for efficacy

- Population assessable for efficacy: All patients eligible and for whom the following conditions are satisfied:
 - Received at least one complete or two incomplete treatment cycles,
 - At least one disease measurement recorded not less than six weeks after treatment onset.
- The following patients will also be included in the population assessable for efficacy; they will be considered as “inevaluable for response” for the primary endpoint as per RECIST v1.1 criteria (i.e. objective response under treatment) and not be replaced in the primary efficacy analysis:
 - Any eligible patients who received at least one treatment cycle or two incomplete treatment cycles and experience disease progression or die due to disease progression prior to response evaluation (will be considered as “inevaluable for response” due to early, progression).
 - Patients withdrawn due to drug-related toxicity without any tumor assessments after the start of study treatment (will be considered as “inevaluable for response” due to toxicity).
 - Patients who received at least one administration of the treatment AND withdrawn due to significant clinical deterioration of unknown reason AND without any tumor assessments after the start of study treatment (will be considered as “inevaluable for response” due to significant clinical deterioration).
- Safety population: all patients having received at least one (any) treatment administration.

CREATION OF A NEW INDICATOR VARIABLE

New binary variable ELI_EFF

Label: « Evaluable for Efficacy »

ELI_EFF=1 if the patient is evaluable for the efficacy analysis

ELI_EFF=0 if the patient is not evaluable for the efficacy analysis

Criteria	eFORM variable	Control
Population evaluable for EFFICACY	ELI_EFF (new variable)	ELI_EFF = 1 IF

 Received one complete or two incomplete treatment cycles 	CYCLE 1 – DAY 1 AND DAY 2 (WEEK1) CYCLE 2 – DAY 1 AND DAY 2 (WEEK1) ADMI_TRA (1=Done) ADMI_DUR (1=Done) VPRE_TRA VOL_TRA VPRE_DUR VOL_DUR INT_TRA INTER_D	Cycle 1 completed $(C1_ADMI_TRA = 1 \text{ and } C1_ADMI_DUR = 1 \text{ and } (C1_VPRE_TRA = C1_VOL_TRA) \text{ and } (C1_VPRE_dur = C1_VOL_dur))$ Or Cycle 1 incomplete and Cycle 2 done $(C1_ADMI_TRA = 1 \text{ and } C1_ADMI_DUR = 1 \text{ and } ((C1_VPRE_TRA \neq C1_VOL_TRA) \text{ or } (C1_VPRE_dur \neq C1_VOL_dur))) \text{ and }$

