3.2.2 Expansion cohorts

- Analyses will be conducted separately for sarcoma and ovarian cancer patients.
- Primary efficacy endpoint will be analysed based on the eligible and assessable population:
 - Each patient will be assigned one of the following categories:
 - Complete response
 - Partial response
 - Stable disease
 - Progression
 - Inevaluable for response
 - The rate of objective response (complete or partial response) under treatment will be reported:
 - All eligible and assessable patients will be included in the denominator for the calculation of the objective response rate (ORR).
 - The 95% two-sided confidence limits will be provided for the ORR (binomial law).
 - First endpoint conclusions will be based on the objective response rate ORR for all eligible and assessable patients (section 10.2) after centralized radiological review of the data.
- As regards to the other efficacy endpoints, the analyses will be carried out in the eligible and assessable population:
 - Each patient will be assigned one of the following categories:
 - Complete response
 - Partial response
 - Stable disease
 - Progression
 - Inevaluable for response
 - The rate of best overall response will be calculated as the number of patients alive with the best response (recorded from the start of the treatment) divided by the number of patients eligible and assessable.
 - The 6-month progression-free rate will be calculated as the number of patients remaining alive and progression-free at 6 months from the start of the treatment divided by the number of patients eligible and assessable.
 - The 6-month objective response rate will be calculated as the number of patients alive with complete or partial response at 6 months divided by the number of patients eligible and assessable.
 - The 95% two-sided confidence limits will be provided for the calculated rates (binomial law)
- The safety analysis will be performed on the safety population.
- Quantitative variables will be described using mean and standard deviations if the normality assumption is satisfied, else other descriptive statistics (median, range, quartiles) will be reported.
- Qualitative variables will be described using frequency, percentage and 95% confidence interval (binomial law).
- Survival endpoints will be analysed using the Kaplan-Meier method. The median survival rates will be reported with a 95% confidence interval. Median follow-up will be calculated using the reverse Kaplan-Meier method.

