3.2.4 Secondary endpoints

For dose escalation part: Only the patients assessable for safety (TOL = 1) will take part into this analysis.

For expansion cohorts: Only the patients evaluable for efficacy (ELI_EFF = 1) will take part into this analysis.

Criteria	eFORM variable	Control
Objective response rate, defined as the rate of complete or partial response according to RECIST v1.1	
ASSE_CYC (TUMOR ASSESSMENT) DT_MEASC (date of measurement) ME1RTLC-ME5 RTLC (measures of lesions) SUM_RTLC (largest diameters) EVA1RLNMC-EVA5 RLNMC (non-measurable lesions eval) RES_RTLC, RES_RNTL (target and non-target lesions) OV_REV (overall response) CR=1, PR=2, SD=3, PD=4, NE=5 New variables : NB_BORR (nb of objective response case)
 
END OF STUDY (END_STU) DT_EOS (date of end of study)
	Status at each TUMOR ASSESSMENT
6-month objective response rate , defined as the rate of complete or partial response at 6 months according to RECIST v1.1	
ASSE_CYC (TUMOR ASSESSMENT) DT_MEASC (date of measurement) ME1RTLC-ME5 RTLC (measures of lesions) SUM_RTLC (largest diameters) EVA1RLNMC-EVA5 RLNMC (non-measurable lesions eval) RES_RTLC, RES_RNTL (target and non-target lesions) OV_REV (overall response) CR=1, PR=2 TREATMENT DT1_START ((Day 1 of treatment)) New variables : NB_ORR (nb of objective response case at 6months)
	DT_START filled in ME1RTLC-ME5 RTLC (filled in if needed) SUM_RTLC C filled in and check recist1.1 criteria EVA1RLNMC-EVA5 RLNMC (filled in if needed) RES_RTLC, RES_RNTL (filled in) Compute number of patients with OV_REV in (1 or 2) at 6 months
6-month Non-progression rate (NPR) defined as the percentage of patients with CR, PR or stable disease (SD) according to RECIST v1.1, (CR, PR or SD more than 24 weeks)	
ASSE_CYC (TUMOR ASSESSMENT) DT_MEASC (date of measurement) ME1RTLC-ME5 RTLC (measures of lesions) SUM_RTLC (largest diameters) EVA1RLNMC_EVA5RLNMC (non-
	DT_START filled in ME1RTLC-ME5 RTLC (filled in if needed) SUM_RTLC C filled in and check recist1.1 criteria EVA1RLNMC-EVA5 RLNMC (filled

	
measurable lesions eval) RES_RTL, RES_RNTL (target and non-target lesions) OV_RESP (overall response) CR=1, PR=2, SD=3 TREATMENT DT1_START ((Day 1 of treatment)) New variables : NB_NPR (nb of non-progression case at 6 months)
	
in if needed) RES_RTL, RES_RNTL (filled in) Compute number of patients with OV_REV in (1 2 3) at 6 month for at least 24 weeks

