4.3.10 Overall survival

Table 10.1 For all patients eligible and assessable for efficacy: Median OS, 6-month OS rate and 1-year OS rate

Table 10.2. For each arm of treatment: Median OS, 6-month OS rate and 1-year OS rate

Figure 2: Kaplan-Meier – OS curves – Patients eligible and assessable for efficacy

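### Escalation PFS, OS and response are analysed in a DLT-evaluable set that drops cycle-1 progressors, and expansion PFS and OS drop some early deaths: a modest, avoidable upward bias in survival

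*SAP*

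**What the plan says.** **Escalation.** SAP 3.2.4 opens with: "For dose escalation part: Only the patients assessable for safety (TOL = 1) will take part into this analysis". The table beneath it covers ORR, the 6-month rates, PFS and OS. SAP 2.3 sets TOL to 0, and has the patient replaced, in two cases. One is a cycle-1 relative dose intensity of 75% or less because of a drug-related event that is not a DLT. The other reads: "Patient goes off treatment over cycle 1 for reasons unrelated to toxicity (DLT or any other AE), e.g. progression, lost to follow-up". Protocol 9.3.2.1 names this population for the escalation primary endpoint only.

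**Expansion.** SAP 3.2.4 continues: "For expansion cohorts: Only the patients evaluable for efficacy (ELI_EFF = 1) will take part into this analysis". The output list agrees, for example "Table 10.1 For all patients eligible and assessable for efficacy: Median OS, 6-month OS rate and 1-year OS rate", and Table 9.1 uses the same set for PFS. Under SAP 2.4, ELI_EFF normally needs a tumour measurement at six weeks or later. Three groups without one are kept as inevaluable. The first begins "Any eligible patients who received at least one treatment cycle or two incomplete treatment cycles and experience disease progression or die due to disease progression". The others are withdrawals for drug-related toxicity and withdrawals for unexplained clinical deterioration. Anyone else who is not assessable is replaced (SAP 2.1.2).

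**Endpoint definitions.** Protocol 8.2 states: "Overall Survival (OS) is defined as the time from study treatment initiation to death (of any cause". PFS has the same start and also counts any death.

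**Primary ORR.** SAP 3.2.2 says: "All eligible and assessable patients will be included in the denominator for the calculation of the objective response rate (ORR". The control column of the expansion table in SAP 3.2.3 is nevertheless headed TOL = 1.

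**The concern.** A time-to-event analysis that starts at first dose should contain everyone who received a first dose. Replacing patients who leave cycle 1 for non-toxic reasons is sensible when DLTs are counted, because they do not complete the observation window. Carried over to PFS, the same rule removes patients for having progressed. The expansion set is better built, since most early failures stay in. It still lets an early death fall out according to its cause, under endpoints that count death from any cause.

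In both parts the survival curves would partly describe patients who got through the first weeks rather than patients who started treatment. The results will be read against other figures: Protocol 1.3.3 itself quotes a 6-month progression-free rate of about 35–40% for trabectedin alone in sarcoma.

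**Working it through.** **1. Who is removed in escalation.** The TOL code in SAP 2.3 applies to patients with treatment ending within 21 days and no DLT, and spares only end-of-treatment reasons 4 and 12. SAP 2.4 shows that code 1 is disease progression and code 12 is progression together with adverse events. Plain progression in cycle 1 therefore gives TOL = 0, as the text says.

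**2. Who is removed in expansion.** Take a treated, eligible patient with no scan at six weeks or later:
- early progression or death from progression: kept;
- withdrawal for drug toxicity: kept;
- withdrawal for unexplained clinical deterioration: kept;
- death from an intercurrent, unrelated or unknown cause: no branch applies, so dropped and replaced.

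The SAP plans no PFS or OS analysis in all treated patients. The safety population serves the safety analysis only.

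**3. The plan's own sizes.**
- Escalation (Protocol 9.1.1): 3 levels × 6 = 18 assessable, 20 accrued; 18/0.9 = 20. Reproduced.
- Expansion: the smallest n with 0.8^n ≤ 0.05 is 14 (0.8^13 = 0.055, 0.8^14 = 0.044). Reproduced. 14/0.9 = 15.6, against 15 recruited; the difference is immaterial here.

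**4. Bound on the bias.** Let q be the share of treated patients who are removed, and suppose all of them had an early event. After those events, S_all(t) = (1 − q) × S_selected(t), so the selected rate is too high by the factor 1/(1 − q).

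| Part | q | Factor | 35% becomes | 40% becomes | 50% becomes |
|---|---|---|---|---|---|
| Escalation, 2 of 20 | 0.100 | 20/18 = 1.11 | 31.5% | 36.0% | 45.0% |
| Expansion, 1 of 15 | 0.067 | 15/14 = 1.07 | 32.7% | 37.3% | 46.7% |

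The differences are 3.5 to 5.0 points in escalation and 2.3 to 3.3 points in expansion. If the selected curve is exponential, the ratio of medians (all to selected) is ln[(1 − q)/0.5]/ln 2: 0.85 in escalation and 0.90 in expansion.

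The escalation factor is for the levels pooled. Within one full dose level, a single removal gives 7/6 = 1.17. The documents state no cap on replacement in expansion: at 2 of 16 a rate of 50% becomes 43.8%, and at 3 of 17 it becomes 41.2%.

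**5. Is q = 0.10 plausible in escalation?** Assume exponential PFS with a 6-month rate of 35–40%. The chance of an event by week 3 is then 1 − 0.35^(3/26) = 11.4% down to 1 − 0.40^(3/26) = 10.0%, about 2 of 20 patients. This is a ceiling, because not every such event ends treatment within 21 days.

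**6. Against sampling error.** At n = 14, 5 responders or survivors give 35.7% (exact 95% CI 12.8–64.9%); 5 of 15 give 33.3% (11.8–61.6%). The shift is small beside the interval.

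**The case against.** The case against runs as follows, and much of it stands.

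- **No decision turns on this.** All analyses are descriptive. The MTD rests on DLTs, the RP2D on safety and pharmacodynamic data (Protocol 3.2), and the expansion rule on at least one response. This stands.
- **Anti-tumour activity belongs to expansion** (Protocol 2.2 and the heading of 7.2). Yet Protocol 8.2 and SAP 3.2.1 still list escalation response, PFS and OS, so they will be reported.
- **In expansion the SAP follows the protocol.** Protocol 9.3.2.2 sets the eligible and assessable population for the other efficacy endpoints. This stands, and it limits what a SAP edit alone can do.
- **Few patients may be affected.** Imaging is six-weekly, so RECIST progression by day 21 needs an unscheduled scan. Protocol 4.4 generally dates discontinuation 30 days after the last dose; if the end-of-treatment date follows that, the 21-day test in the TOL code would miss most of the patients whom the text removes. This lowers the likely size, but it is itself a mismatch between text and code.

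Four stronger readings are tempting but not supported:

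- **That every exclusion is favourable.** Exclusions for low dose intensity, ineligibility or loss to follow-up have no fixed direction.
- **That response rates are inflated throughout.** In expansion, early progression, toxicity and deterioration stay in the ORR denominator. In escalation, response is given as counts by dose level (SAP 3.2.1), so only the general percentages of SAP 3.1 and the progression and inevaluable cells are exposed.
- **That Appendix 3 sets a rival denominator**, since it says that only patients who, among other conditions, "have received at least one cycle of therapy, and have had their disease re-evaluated will be considered evaluable for response". Its following note keeps patients who progress before the end of cycle 1, and Protocol 9.2.2 and 9.3.2.2 fix the denominator.
- **That the primary ORR is meant to be run on TOL = 1.** TOL is defined for escalation only, and SAP 3.2.2 and Tables 6.1, 6.2 and 6.4 say otherwise. The heading looks like a copied label. It still contradicts SAP 3.2.2 on the primary endpoint.

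**Conclusion.** The point holds and should be fixed, but it is not critical. Escalation PFS is conditioned on not having left treatment through progression in cycle 1, and the protocol does not ask for that. Expansion PFS and OS omit a narrow class of early deaths that their definitions count. Removing early events biases the survival estimates upward.

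The bounds in the working assume that every patient in the plan's non-assessable allowance was removed for an early event; the lower bound is no effect at all. For escalation OS the true effect lies below the bound if the removed progressors live on. If replacement exceeds the allowance, the effect grows.

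**What to change.** - **(a) SAP 3.2.4, escalation.** Analyse PFS and OS in all treated patients from first dose, and response in all treated eligible patients. Keep TOL = 1 for the DLT and primary safety analysis only. The flag SAF is defined under the expansion heading (SAP 2.4), so state that it is computed for both parts.
- **(b) SAP 3.2.4 and Tables 9.1–10.2, expansion.** Report PFS and OS in all treated patients by cohort, alongside the eligible and assessable set that Protocol 9.3.2.2 requires. Making all treated patients the main set would need a matching protocol change.
- **(c) SAP 3.2.3, expansion table.** Replace TOL = 1 by eligible and ELI_EFF = 1, to agree with SAP 3.2.2.
- **Code to reconcile at the same time.** The 21-day test for TOL should be squared with the discontinuation date in Protocol 4.4. The early-progression branch of ELI_EFF requires a blank measurement date, so progression seen on a scan before week 6 may fit no branch, although the text keeps it.

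No new data are needed: Protocol 4.9 already follows patients after treatment for progression and death. The cost is one extra set of tables and slightly less favourable rates.

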2.1.2 Expansion cohorts

- Eligible population: All patients included without major violation of eligibility criteria.
- Population assessable for efficacy: All patients eligible and for whom the following conditions are statisfied:
 - Received at least one complete or two incomplete treatment cycles,

- At least one disease measurement recorded not less than six weeks after treatment onset.
- The following patients will also be included in the population assessable for efficacy; they will be considered as “inevaluable for response” for the primary endpoint as per RECIST v1.1 criteria (i.e. objective response under treatment) and not be replaced in the primary efficacy analysis:
 - Any eligible patients who received at least one treatment cycle or two incomplete treatment cycles and experience disease progression or die due to disease progression prior to response evaluation (will be considered as “inevaluable for response” due to early, progression).
 - Patients withdrawn due to drug-related toxicity without any tumor assessments after the start of study treatment (will be considered as “inevaluable for response” due to toxicity).
 - Patients who received at least one administration of the treatment AND withdrawn due to significant clinical deterioration of unknown reason AND without any tumor assessments after the start of study treatment (will be considered as “inevaluable for response” due to significant clinical deterioration).
- Safety population: all patients having received at least one (any) treatment administration.

Patient's replacement:

- Any patient not eligible or not assessable for efficacy will be replaced.
- However, any patient who received at least one administration of the study drug will be included in the safety analysis.

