2.2.4 Eligible population

- Eligible population: All patients included without major violation of eligibility criteria.

Criteria	eFORM variable	Program (SAS)
Eligible Population	ELIGIBILITY FORM C1I C2I C3I C4I C5I C6I C7I C8I C9I C10I C11I C12I C13I C14I C15I C16I C17I C1NI C2NI C3NI C4NI C5NI C6NI C7NI C8NI C9NI C10NI C11NI C12NI C13NI C14NI C15NI C16NI C17NI	ELI=1 If (C1I = 0 or C2I = 0 or C3I = 0 or C4I = 0 or C5I = 0 or C6I = 0 or C7I = 0 or C8I = 0 or C9I = 0 or C10I = 0 or C11I = 0 or C12I = 0 or C13I = 0 or C14I = 0 or C15I = 0 or C16I = 0 or C17I = 0 or C1NI = 1 or C2NI = 1 or C3NI = 1 or C4NI = 1 or C5NI = 1 or C6NI = 1 or C7NI = 1 or C8NI = 1 or C9NI = 1 or C10NI = 1 or C11NI = 1 or C12NI = 1 or C13NI = 1 or C14NI = 1 or C15NI = 1 or C16NI = 1 or C17NI = 1) then ELI=0

CREATION OF A NEW INDICATOR VARIABLE

Patients fulfilling inclusion and non-inclusion criteria will be considered as **ELIGIBLE (ELI=1)**.

New binary variable ELI

Label: « Eligibility based on CRF»

ELI=1 if the patient is eligible

ELI=0 if the patient is not eligible

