		$((C2_ADMI_TRA = 1 \text{ or } C2_ADMI_DUR = 1) \text{ and } (C2_VOL_TRA > 0 \text{ or } C2_VOL_TRA > 0))$ Additional control: Date of start cycle Total dose given during cycle Therapy changes during cycle AND

 one disease measurement recorded not less than six weeks after treatment onset 	TUMOR ASSESSMENT (TUM_CYC) DIS_EVA (1=week 6) DT_MEAC	DIS_EVA =1 and Information on tumor assessment completed and date of tumor assessment OR IF
❖ Received at least one treatment cycle and experience disease progression or die due to disease progression prior to response evaluation after the start of study treatment	CYCLE 1 – DAY 1 AND DAY 2 (WEEK1) ADMI_TRA (1=Done) ADMI_DUR (1=Done) TREATMENT (EOTRT) EOTREASO (1=Disease progression and 12=Disease progression and Adverse event(s)) END OF STUDY (EOS) REA_STUD (3=Death) DT_DEATH CA_DEATH (1= Progression of disease) TUMOR ASSESSMENT (TUM_CYC) DT_MEAC (Date of measurement)	(C1_ADMI_TRA = 1 and C1_ADMI_DUR = 1) Additional control: Date of start cycle Total dose given during cycle Therapy changes during cycle AND $((EOTREASO \text{ in } (1 \text{ 12}) \text{ or } (CA_DEATH=1 \text{ and } EOS_REA = 3)) \text{ and } DT_MEAC \text{ is blank})$ OR IF
❖ withdrawn due to drug-related toxicity without any tumor assessments after the start of study treatment	DISCONTINUATION VISIT TRA_EOT (0=toxicity) DUR_EOT (0=toxicity) TUMOR ASSESSMENT (TUM_CYC) DT_MEAC (Date of measurement)	DT_MEAC is blank AND TRA_EOT =0 or DUR_EOT=0 OR IF
❖ Patients who received at least one administration of the treatment AND withdrawn due to significant clinical deterioration of unknown reason AND without any tumor assessments after the start of study treatment	TUMOR ASSESSMENT (TUM_CYC) DT_MEAC (Date of measurement) DISCONTINUATION VISIT END OF TREATMENT (EOTRT) DT_SOT, DT_EOT (start and end of treatment) EOTREASO (8= General or specific changes in patient's condition) ADVERSE EVENT FORM (AEV) DT_AE, DTENDAE (start and end date) TRA_MOD (3= Definitively stopped) DUR_MOD (3= Definitively stopped) TRA_REL (2= Unrelated) DUR_REL (2= Unrelated)	DT_MEAC is blank EOTREASO = 8

- Safety population: all patients having received at least one (any) treatment administration

CREATION OF A NEW INDICATOR VARIABLE

Patients will be evaluable for safety if they have received at least one treatment administration. (SAF=1).

New binary variable ELI_DLT

Label: « Safety population»

SAF=1 if the patient is assessable for safety

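### The SAP's efficacy flag for the expansion cohorts (ELI_EFF) never tests eligibility, so its program contradicts the SAP's own eligible-and-assessable population

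*SAP*

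**What the plan says.** **The population in words.** SAP 2.4 defines it as: "Population assessable for efficacy: All patients eligible and for whom the following conditions are satisfied". Protocol 9.2.2 has the same rule. SAP 3.2.2 states: "Primary efficacy endpoint will be analysed based on the eligible and assessable population". It applies the same restriction to the other efficacy endpoints, as does protocol 9.3.2.2.

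**The eligibility flag.** SAP 2.2.4 builds `ELI` from the inclusion and non-inclusion items: "ELI=0 if the patient is not eligible".

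**The efficacy flag.** SAP 2.4 then creates a second variable: "ELI_EFF=1 if the patient is evaluable for the efficacy analysis". Its control column gives four alternative routes, none of which mentions `ELI`.

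**The filters.** For the secondary endpoints, SAP 3.2.4 states: "For expansion cohorts: Only the patients evaluable for efficacy (ELI_EFF = 1) will take part into this analysis". For the expansion primary endpoint, the table in SAP 3.2.3 is headed TOL=1, a flag that SAP 2.3 defines for the dose-escalation part.

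**Replacement.** SAP 2.1.2 states: "Any patient not eligible or not assessable for efficacy will be replaced". The same section also places this group in the efficacy population and says its members are not replaced, without requiring eligibility: "Patients withdrawn due to drug-related toxicity without any tumor assessments after the start of study treatment". The clinical-deterioration clause is worded in the same way.

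**The concern.** The eligibility flag is derived and then never used in any derivation or filter for the expansion efficacy analyses. A programmer who follows the control columns obtains a different population from the one in the text. Because ineligible patients are replaced, both the ineligible patient and the replacement would be analysed.

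The prose also conflicts with itself in one place. An ineligible patient withdrawn for toxicity is kept and not replaced under one clause, and replaced under another.

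At stake are the 6-month ORR, 6-month PFR, PFS and OS, which the SAP 3.2.4 filter governs directly. The ORR is at stake as well if either `ELI_EFF` or `TOL` selects its population. Protocol 9.1.1 (expansion cohorts) calls the combination worthy of further testing after a single response, so even one misclassified patient can matter.

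**Working it through.** **1. Text against program in SAP 2.4**

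| Route to ELI_EFF=1 | Prose requires eligibility? | Program tests `ELI`? |
|---|---|---|
| Exposure plus week-6 assessment | Yes | No |
| Early progression | Yes | No |
| Withdrawal for toxicity | Not stated | No |
| Clinical deterioration | Not stated | No |

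In the early-progression row the program label even drops the word that the prose contains: "Received at least one treatment cycle and experience disease progression or die due to disease progression prior to response evaluation".

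**2. Can the condition be taken as implicit?** Where the SAP applies a population condition, it writes it down. SCR_PT=0 heads the eligibility control columns in SAP 2.2.2 and 2.2.3, and TOL=1 heads the tables in SAP 3.2.3. SCR_PT removes screening failures only. `TOL` (SAP 2.3) depends on cycle-1 dose intensity and on stopping during cycle 1, not on eligibility.

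**3. Trace one patient.** Suppose prior anti-PD-1 therapy is found after entry.
- Non-inclusion item 1 fails, so ELI=0.
- Protocol 4.4 requires stopping on this ground only if continuing might be a safety risk, so the patient may complete cycle 1 and have the week-6 scan.
- The first route gives ELI_EFF=1, and the SAP 3.2.4 filter keeps the patient.
- The replacement also has ELI_EFF=1. Both are analysed.

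**4. Reproduce the planned size.** Inputs from protocol 9.1.1 (expansion cohorts): 20% efficacy rate, 5% error, at least one response needed. The Gehan first stage is the smallest n with (1 − 0.20)^n ≤ 0.05.
- 0.8^13 = 0.0550, too large.
- 0.8^14 = 0.0440, so n = 14, as stated.

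**5. Chance that one ineligible patient alone changes the decision.** Assume 14 eligible and assessable patients, one ineligible evaluable patient, and the same true ORR p in both. The rule flips from 0/14 to 1/15 with probability (1 − p)^14 × p.

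| True ORR | (1 − p)^14 | × p | Flip |
|---|---|---|---|
| 5% | 0.4877 | × 0.05 | 2.4% |
| 10% | 0.2288 | × 0.10 | 2.3% |
| 20% | 0.0440 | × 0.20 | 0.9% |

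These figures are conditional on such a patient existing. The documents give no ineligibility rate. If it were 2%, 5% or 10%, the chance of at least one ineligible patient among 15 would be 1 − (1 − q)^15 = 26%, 54% or 79%. Not every such patient would be treated and evaluable.

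**6. Effect on the estimate (exact 95% intervals).** Suppose one of the 14 eligible patients responds: 1/14 = 7.1% (0.2 to 33.9). Adding one ineligible patient gives 1/15 = 6.7% (0.2 to 31.9) if that patient does not respond, or 2/15 = 13.3% (1.7 to 40.5) if the patient does.

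**The case against.** The strongest reply is that the governing text already requires eligibility. SAP 3.2.2 and protocol 9.3.2.2 set the eligible-and-assessable population for the primary and the other efficacy endpoints. The main output titles in SAP 4.3.6 to 4.3.10 repeat it, and Table 1.3 counts eligible patients separately from those who are also assessable. The control column mixes field checks with logic and is not finished code. Eligible patients are entered centrally (protocol 5.2), and selection criteria are checked for every patient (protocol 11.2.2). All of this stands. It makes the error avoidable, but the program specification remains wrong.

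Four stronger readings are tempting, and the documents do not support them.
- **That ineligible patients will be in the efficacy analyses.** This follows only if the control columns are run literally, against the text and table titles, and at least one ineligible patient is treated and evaluable.
- **That `ELI_EFF` decides go or no-go.** The primary table is headed TOL=1, and the prose limits the primary analysis to eligible patients. An ORR row does appear in SAP 3.2.4, but under secondary endpoints.
- **That one or two ineligible patients per cohort should be expected.** The 10% allowance covers ineligible and non-assessable patients together: 0.10 × 15 = 1.5 for both reasons. Nor is a denominator of 15 a sign of error, since 15 are recruited and all may qualify.
- **That a tumour found not to be sarcoma on central pathology review would slip in.** Protocol 7.1.1 says such patients are not included.

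A further objection concerns the remedy. `ELI` as coded is 0 for any failed criterion, while the population is defined by absence of a major violation, and the code omits item C18NI. This is right: adding `ELI` unchanged would create a new mismatch.

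**Conclusion.** The point holds as an inconsistency between the SAP's text and its program. `ELI` is derived, no route to `ELI_EFF` tests it, and the filters in SAP 3.2.3 and 3.2.4 do not supply it. The toxicity and deterioration clauses also conflict with the replacement rule.

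The direct exposure is in the secondary endpoints. For the one-response rule the effect is conditional and small: about 2% per cohort at a true ORR of 5% to 10%, and under 1% at the design rate of 20%. That rests on literal programming, exactly one ineligible evaluable patient, 14 eligible ones, and a common response rate. It should be corrected because the repair is cheap and a single response settles the conclusion for a cohort.

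**What to change.** 1. **Align `ELI` first (SAP 2.2.4).** State which deviations count as major violations, derive `ELI` from those, and include C18NI.
2. **Correct `ELI_EFF` (SAP 2.4).** Set ELI_EFF=1 only if ELI=1 AND (route 1 OR route 2 OR route 3 OR route 4). The brackets matter because the routes are joined by OR.
3. **Use the corrected flag throughout the expansion part.** In SAP 3.2.3 replace TOL=1 with ELI_EFF=1 for the expansion table. In SAP 3.2.4 keep the filter on the corrected flag.
4. **Align the prose.** Insert the word eligible in the toxicity and deterioration clauses of SAP 2.1.2 and 2.4 and of protocol 9.2.2, so that they agree with the replacement rule.

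The cost is one bracketed condition, one table header, one missing item, one word in two clauses wherever they appear, and a short agreed list of major violations. That list is the only part needing discussion. No extra patients or data are needed.
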